The potential risks associated with this study have to do with maintenance of the confidentiality of the identities of the participants enrolled in the study and information relating to them. As with all of our studies, we will train study researchers in maintaining confidentiality. Prior to the start of the focus group, researchers will discuss potential risks including breach of confidentiality. Examples include but are not limited to informing participants at the beginning of focus groups of risks related to confidentiality and the sensitive nature of the topic, by conducting focus groups in a private classroom in the school, by training and reviewing questions with our team of experts who specialize in addiction medicine, and by informing study participants via information sheets of the risks of confidentiality breaches. Discussion topics will focus on interested content to build out narratives for game development. Participants will be encouraged to only disclose what they are comfortable sharing and to consider sharing suggestions for building out a videogame intervention as opposed to confidential information about themselves. De-identified hard copies of any data will be stored in locked cabinets and electronic data will be stored in secure, password-protected computers. Only the PI and other relevant research staff will have access to the data.

Playing the **PlaySmart** game or engagement in discussions with the research team about its content may pose a potential psychological risk in that we address sensitive issues around drug use and its consequences. The research staff will be available to provide assistance to all participants, answer their questions, and serve as a resource if any distress or concern arises. The assessments and instruments may also present a potential risk given that some of the questions are sensitive in nature and address issues around drug use and risky behaviors. Again, the research staff will be available to assist the participants and the program site staff if there appears to be any distress around the questions being asked and connect them to appropriate school personnel.

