If there are concerns about issues raised with regards to substance use or mental health, or if participants need additional or more intensive attention, the research staff will contact [name] or [name] (who is a Licensed Professional Counselor and has extensive expertise working with adolescents and schools) who will discuss providing further consultation to the participant.

It is anticipated that the adolescents enrolled in this study should benefit directly from the study as the purpose of the study is to facilitate increasing their perception of risk of harm from initiating the misuse of opioids, decreasing their actual misuse of opioids, as well as improving their decision making and knowledge to optimize their abilities to negotiate around risky behaviors. The potential benefits to participants are great while strict precautions are being taken to protect the confidentiality and well-being of participants, as has been described above. Thus, the potential benefits to the participants outweigh the potential risks.

10. **Minimizing Risks:** Describe the manner in which the above-mentioned risks will be minimized.

This study presents minimal risks to the participants and adverse events or other problems are not anticipated.

Adverse Events (AEs):

Violation of confidentiality: Any breach of confidentiality.

Discomfort due to assessment procedures: Discomfort created by answering survey questions.

Embarrassment in disclosing sensitive personal information.

Disclosure of information about current and/or intended physical harm to persons; current and/or intended abuse of children that would be reported to a child welfare agency; and/or an investigation of such allegation(s) that could ensue.

Dissatisfaction with the intervention activities: In this case it would be the game intervention.

While gaming addiction is a recognized entity, it is very rare and, in the setting of playing a serious game, very unlikely. If there are any concerns of developing serious addictive behaviors in our pilot study participants, we have team members who are experts in the field of addiction medicine and will address these issues immediately.

Serious Adverse Events (SAEs):

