SAEs include death, life threatening injury or condition, hospitalization, persistent or significant disability/incapacity, and other conditions which in the judgment of the investigators represent significant hazards. In the rare event of an SAE, we do not expect them to be related to our study.

Procedures for research team management of AEs, SAEs and other study risks such as mandatory reporting requirements:

This study presents minimal risks to the participants and adverse events or other problems are not anticipated. In the unlikely event that such events occur, Reportable Adverse Events (which are events that are serious or life-threatening and unanticipated (or anticipated but occurring with a greater frequency than expected) and possibly, probably, or definitely related) or unanticipated problems involving risks to subjects or others will be reported in writing within 48 hours to the IRB (using the appropriate forms from the website) and the NIDA PO. The PI will apprise fellow investigators and study personnel of all adverse events that occur during the conduct of this research project through regular study meetings and via email as they are reviewed by the PI. We will use procedures to detect and respond to adverse events that ensure prompt discovery of any adverse events and to minimize their effects. There is adequate surveillance and protections to discover adverse events promptly and keep their effects minimal.

Procedures for training and supervision of all research personnel have been developed as part of our previous and current studies. All members of the research team are familiar with procedures for identifying and reporting possible adverse reactions. All members of the research team are trained in mandatory reporting and will notify the PI immediately of any concerns raised about participant mental health (suicidality), substance use, abuse of any kind, and so forth.

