If an adverse event occurs study personnel will notify the PI as well as the appropriate Information Security Officer (ISO) and follow all necessary procedures. All adverse events are reported using the Yale Institutional Review Board (IRB) standard template for reporting adverse events. The PI reviews all adverse events, classifies the attribution of adverse events (e.g., definitely, probably, possibly related; unlikely or unrelated) and grades the severity of the event, utilizing the FDA's definition of serious adverse events, on a 6-point scale (0=no adverse event or within normal limit; 1=mild; 2=moderate; 3=severe; 4=life-threatening; 5=fatal). Serious unanticipated or anticipated adverse events will be reported immediately to the IRB and to the NIDA PO within 24 hours by phone and/or email and will submit a written report to the PO no more than two days later. Adverse events will be reported in summary form at least annually to the IRB. The summary will include the number of participants enrolled and a summary of graded adverse events to date, using the chart format included in the Yale University DSMP template. The PI will evaluate all adverse events and determine whether the event affects the Risk/Benefit ratio of the study and whether modifications to the protocol (e.g., Risks to Subjects) or consent form (e.g., Risks and Inconveniences) are required.

The PI will be responsible for monitoring the data and conducting performance and safety reviews, at the specified frequency. Either the PI or the IRB have the authority to stop or modify the study. The monitoring by the IRB will occur annually at the time of re-approval. The PI will conduct data and safety review at least quarterly and at any time a serious adverse event occurs. During the review process, the PI will evaluate whether the study should continue unchanged, requires modification or amendment to continue, or should be closed to enrollment.

11. Data and Safety Monitoring Plan: Include an appropriate Data and Safety Monitoring Plan (DSMP) based on the investigator's risk assessment stated below. (Note: the HIC will make the final determination of the risk to subjects.)

a. What is the investigator's assessment of the overall risk level for subjects participating in this

- b. study? Minimal risk
- c. If children are involved, what is the investigator's assessment of the overall risk level for the children participating in this study? Minimal risk

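### Discomfort and embarrassment are listed as adverse events, but every detection route the plan describes is passive, so they may be under-counted

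*Combined protocol and SAP*

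**What the plan says.** Item 10 (Minimizing Risks) names the adverse events to be recorded. Two are states that a participant can have without showing them: "Discomfort due to assessment procedures: Discomfort created by answering survey questions" and "Embarrassment in disclosing sensitive personal information". The same item has the PI grade every event on a 0 to 5 scale on which 1 is mild, and requires at least a yearly summary to the IRB giving graded events and the number enrolled. It adds that "The PI will evaluate all adverse events and determine whether the event affects the Risk/Benefit ratio of the study".

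On finding events, item 9 (Risks) gives two routes. For the assessments, "the research staff will be available to assist the participants and the program site staff if there appears to be any distress". For game play and discussions, staff are there to help all participants and "serve as a resource if any distress or concern arises". Item 10 adds that team members "will notify the PI immediately of any concerns raised about participant mental health (suicidality), substance use, abuse of any kind".

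Item 10 also makes two general statements: "We will use procedures to detect and respond to adverse events that ensure prompt discovery of any adverse events" and "There is adequate surveillance and protections to discover adverse events promptly and keep their effects minimal". Neither is followed by a description of what is done.

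**The concern.** The plan sets out to count mild, subjective events but describes no step in which a participant is asked about them. An adolescent who is upset by a question on drug use and says nothing produces no record under any described route. Two things are at stake.

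- **Interpretation.** The yearly summary relates graded events to the number enrolled. If few events appear, a reader cannot tell whether few occurred or few were noticed.
- **Participant safety.** Item 9 already provides for further consultation when a participant needs more attention, but that step starts only once staff know of the problem.

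The pilot is also meant to try out procedures for the later randomised trial (item 4, Research Plan, pilot work, item d). How adverse events are ascertained is one of those procedures.

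**Working it through.** **1. Are mild subjective events meant to be counted?** Yes. Item 10 lists them as adverse events, the grading scale has a mild category, and the yearly summary covers all graded events.

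**2. What starts each described route?**

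- Assessments (item 9): distress that is apparent to staff.
- Game play and discussion (item 9): a distress or concern that arises. This is open to self-report, but the participant must take the initiative.
- Escalation to the PI (item 10): a concern that has already been raised.
- General procedures and surveillance (item 10): asserted, with no question, form, time point or person named.

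All the described routes are passive. Section IV (Data entry methods) also lets participants enter their own answers, with a research assistant supervising only where needed. Staff may therefore not be watching during the very procedure that item 10 links to discomfort.

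**3. Do the planned instruments fill the gap?** Item 4 gives pilot players a post-assessment and feedback after play, and Section VI (Payments) mentions follow-up questions in both modes. The stated targets are feasibility, acceptability and usability. No adverse event item is stated. The measures were still being finalised (item 4, formative work, item g).

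**4. The plan's own figure.** Item 6 (Subject Population) has 2 virtual groups of 3 and 6 in-person groups of 4: 2 × 3 + 6 × 4 = 6 + 24 = 30, which matches the stated pilot size. Virtual players are 6/30 = 20%. On the session lengths in Section VI they contribute 6 × 6 = 36 play-hours against 24 × 2 = 48 in person, or 36/84 = 43%. Item 4 describes the sessions differently (two gameplay sessions), so the 43% depends on how those two sections are reconciled.

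**5. What could a count of zero mean?** The plan gives no event rate and no detection rate, so every rate below is an assumption.

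With 0 events recorded in n players, the one-sided 95% upper limit under full detection is 1 − 0.05^(1/n):

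- n = 30: 9.5%
- n = 24: 11.7%
- n = 6: 39.3%

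If only a share s of events is detected, the limit on the true rate is the full-detection limit divided by s. For n = 30 this gives 0.095/0.5 = 19% and 0.095/0.3 = 32%.

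With true rate p, the chance of recording nothing in 30 is (1 − p·s)^30. For p = 10%:

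- s = 1: 0.90^30 = 4%
- s = 0.5: 0.95^30 = 21%
- s = 0.25: 0.975^30 = 47%

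Over p = 5% to 30% and s = 25% to 75%, 1.5 to 9 expected true events would give about 0.4 to 6.8 recorded ones.

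**6. By mode.** With p = 10% and half detected in both modes, the expected number missed is 24 × 0.1 × 0.5 = 1.2 in person and 6 × 0.1 × 0.5 = 0.3 virtually. A larger missed share among virtual players appears only if lower detection is assumed for them. The documents give no basis for choosing that value.

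**The case against.** Four points are made on the other side.

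- **Visible distress is not the only route.** A reader might infer that it is. Item 9 also makes staff a resource for any concern, which allows self-report, and item 10 has concerns passed on. The sentence about apparent distress is mainly a support and referral statement tied to the assessment questions. This stands: the supportable claim is that the described routes are passive and the asserted procedures have no content.
- **The instruments are not in the documents.** They may contain suitable items, and acceptability questions could reach dissatisfaction with the game, which is also a listed event. This stands in part. The absence is shown for the protocol text, not for the questionnaires. But the text also gives no rule by which an answer would become a recorded event.
- **Worse detection in virtual players is conjecture.** A reader might infer it from the screen setting. The documents do not say how virtual sessions are observed, and what they do say is mixed: virtual groups are smaller (3 against 4), and Section VI gives those players six sessions rather than one, so more occasions to speak up. On the other side, the support named in item 9 is largely school-based. This objection stands.
- **The consequence is limited.** The study is assessed as minimal risk, estimating an event rate is not an objective, and the PI's risk/benefit judgement is made event by event rather than from a rate. This stands as a limit on importance. It does not remove the gap, because an event that is never recorded cannot be judged, and the yearly summary does report counts.

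**Conclusion.** The concern holds in a limited form. The plan counts discomfort and embarrassment as adverse events, describes only passive ways of learning of them, and leaves its general detection procedures unspecified. Under-counting is a plausible risk, not a documented fact, and some distressed adolescents could go unnoticed. Its size cannot be computed from the plan. The 19% and 32% limits and the 21% and 47% probabilities rest on assumed detection rates, on a hypothetical zero count or on an assumed 10% event rate. They show only that a clean table would be hard to interpret. Even full detection in 30 players leaves a limit of 9.5%. The documents do not support a statement that detection is worse in the 6 virtual players. This is an inexpensive improvement to a minimal-risk pilot, not a flaw that undermines it.

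**What to change.** Add two or three fixed yes/no items, put to every pilot participant at the end of each session and in the post-assessment, in the same form for both modes: upset by the questions, upset by the game, wants to talk to someone. Record the answers in REDCap under the study number. Send positive answers to the consultation route already in item 9, and state how a positive answer becomes a graded event under item 10. In the yearly summary, report solicited and staff-observed events separately and by mode, with denominators 6 and 24. State in item 10 who is responsible for this, and reconcile the session counts in item 4 and Section VI so that the time points are defined.

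The cost is a few questionnaire items, added while the measures are being finalised. The reported adverse event rate will be higher, so the summary should explain that solicited counts are not comparable with staff-observed ones. Some participants may still not disclose, so the items should improve detection without guaranteeing it.

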
Our study's specific aims are to:

- 1a: Develop the *PlaySmart* game through focus groups with up to 40 16-19-year old high school students, focus groups with up to 20 18-25-year-old young adults, interviews with up to 20 16-25-year olds, interviews with up to 20 opioid use disorder treatment providers and focus groups with up to 20 stakeholders (educators, prevention specialists, etc.).
- 1b: Pilot-test *PlaySmart* with 30 adolescents, using methods from our prior research ^{13,16,19,20,33}
- 1c: Develop implementation strategies and partners through focus groups with 50 School Based Health Alliance affiliates and 30 adolescents from the Youth Advisory Council.

4. **Research Plan:** Summarize the study design and research procedures using non-technical language that can be readily understood by someone outside the discipline. **Be sure to distinguish between standard of care vs. research procedures when applicable and include any flowcharts of visits specifying their individual times and lengths.** Describe the setting in which the research will take place.

This protocol will be conducted over two years. The outline below highlights the research plan. We will conduct focus groups and interviews to help inform the development of a digital intervention and then evaluate the feasibility, acceptability, and usability in a pilot study. Eight focus groups with five adolescents (n=40), aged 16-19, will be conducted locally over the course of six months. Each group will meet once for approximately 1-1.5 hours after school in a classroom. When the study is introduced to parents/guardians and students, we have always stressed that a stipulation of our studies requires reliable transportation to/from our studies. In certain cases where transportation is not available, we will provide a bus pass.

In addition, we will conduct 4 focus groups with approximately five 18-25-year-old young adults (n=20). Each focus group will meet once for approximately 1-1.5 hours at a private location on a college campus, a public meeting space such as a library, or in a location at Yale Medical School. All participants will provide consent. Our goal is to learn about the perceptions and experiences of opioid misuse among young adults to inform our intervention.

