- a.) We will work iteratively to develop videogame content, conducting 8 focus groups of 5 adolescents each (n=40), aged 16-19 and 4 focus groups of 5 young adults each (n=20), aged 18-25 collecting qualitative data for the videogame intervention and to refine our logic model.
- b.) Working with our community school partners, we will engage 1-2 schools and school-

based health centers to **recruit** 30 adolescents for our subsequent pilot study. Given participants are only involved in the pilot study for several weeks and given our track record of having retained the majority of participants for over two years of a prior RCT, we are not concerned about retention.

- c.) We will **pilot-test** the intervention with 30 adolescents, aged 16-19, in conjunction with their schools, to evaluate the **acceptability** of the game. To garner feedback, we will collect data (both qualitative and quantitative) after the completion of game play sessions. The pilot will either be conducted virtually or in person. For the in person segment of the pilot, all COVID-19 protocols and procedures that are in place at our partner school site will be followed.
- d.) We will also **pilot procedures** such as assuring the gameplay sessions go smoothly and that data collection is streamlined in anticipation of conducting the subsequent RCT.
- e.) We will develop a game implementation manual that will be used during the subsequent RCT, as needed, by school and school-based health center staff.
- f.) As part of our focus groups with school-based health affiliates, we will collect focus group data for our formative and development of a videogame intervention from the Youth Advisory Council (n=15) and School-based health affiliates (n=25) at the annual School-Based Health Alliance Convention. This includes data on implementation strategies such as barriers and facilitators and to share perceptions of the newly created game and provide input on the game implementation manual. This will take place at the annual School-Based Health Alliance Convention with our national partners who will help recruit participants for the Youth Advisory Council and School-Based Health Alliance.

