The subject population for this project is adolescents between the ages of 16-19. Young adults aged 18-25 will be recruited for focus groups as well. There are also adults (19-80) that will be recruited to participate in separate focus groups at the Convention.

For this study, 8 focus groups of 5 adolescents each (n = 40), boys and girls in Connecticut, aged 16-19 will participate in the focus groups and 30 adolescents, boys and girls, aged 16-19 will participate in the pilot testing of the adapted game (2 groups of 3 adolescents will participate virtually and 6 groups of 4 adolescents each will participate in person at their school site while following COVID-19 guidelines). These adolescents will be recruited from the high schools that we already have established partnerships with, such as Maloney High and Hamden High. In addition, we will conduct 4 focus groups of young adults aged 18-25 (N=20) in Connecticut. These young adults will be recruited from local universities. Additionally, 30 youth (16-19) over the course of two years (e.g., meeting annually) from the national School-Based Health Alliance (SBHA) National Convention will also be recruited to participate in focus groups for the project.

For the focus groups with the adults, 50 adults (19-80) who are affiliates of the SBHA will be recruited over the course of two years (e.g., meeting annually) during the national SBHA Convention to participate in the project and will receive information sheets. Their role represents various positions within school-based health centers across the nation. Their role in this study is to be part of our focus groups to help inform game development and implementation strategies.

For the individual interviews, up to 20 participants aged 16-25 who are currently receiving treatment for opioid use disorder will be recruited to participate in this study. The Director of Research at the APT Foundation has approved and will post flyers (see example of the flyer attached) on site at the APT Foundation. Other interview participants may be recruited through provider referral. Interested participants will contact our research team to participate.

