- a. Targeted for enrollment at Yale for this protocol: 150
- b. If this is a multi-site study, give the total number of subjects targeted across all sites: *Write here*

2. Indicate recruitment methods below. Attach copies of any recruitment materials that will be used.

181 Flyers	 InterneUwebpostings	D Radio
181 Posters	 Massemail solicitation	 Telephone
 Letter	 Departmental/Center website	D Television
 Medical record review*	D Departmental/Center research boards	D Newspaper
 Departmental/Center newsletters	D Web-based clinical trial registries	D Clinicaltrials.gov
 YCCI Recruitment database	 Social Media(Twitter/Facebook):	

181 Other: Meeting with school and program staff, school orientations and open houses, announcements in schools, also SBHA representative send emails to affiliates and YAC for the Convention

* Requests for medical records should be made through JDAT as described at <http://medicine.yale.edu/ycci/oncore/availableservices/datarequests/datarequests.aspx>

3. Recruitment Procedures:

- a. Describe how potential subjects will be identified. *Write here*
- b. Describe how potential subjects are contacted. *Write here*

Who is recruiting potential subjects? *Write here*

For game development focus groups, students will be recruited through flyers and announcements to the student general population via school meetings and physical education/health classes. Members of our team will also make lunchroom and classroom announcements about our project. We will also ask school teachers/administrators to share announcements about our study to their students. Potentially interested students will receive an information sheet describing the purpose of the research activity and they will be able to agree or decline.

For the young adult focus groups, participants will be recruited through flyers and announcements. Interested participants will be encouraged to contact our team through a number on the flyer. We will work with local universities to follow their protocols in recruiting participants from their school.

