Additionally, we will also recruit adult participants from the annual School-Based Health Alliance Annual Convention to participate in focus groups and/or interviews. Adult participants represent a sample of school-based health centers across the nation. Potentially interested affiliates/attendees will receive information sheets describing the purpose of the research activity and they will be able to agree or decline.

The research study team will carry out all recruitment procedures.

4. Assessment of Current Health Provider Relationship for HIPAA Consideration:

Does the investigator or any member of the research team have a direct existing clinical relationship with any potential subject?

- Yes, all subjects
- Yes, some of the subjects

rgJNo

If yes, describe the nature of this relationship. *Write here*

5. Request for waiver of HIPAA authorization: (When requesting a waiver of HIPAA Authorization for either the entire study, or for recruitment purposes only. Note: if you are collecting PHI as part of a phone or email screen, you must request a HIPAA waiver for recruitment purposes.)

Choose one:

181 For entire study for focus groups (including telephone screening when verbal authorization will be obtained, and later subject will be consented verbally).

181 For recruitment/screening purposes only for pilot group

For inclusion of non-English speaking subject if short form is being used and there is not translated HIPAA research authorization form available on the University's HIPAA website at hipaa.yale.edu.

- i. Describe why it would be impracticable to obtain the subject's authorization for use/disclosure of this data: only waiver of signed authorization is requested
- ii. If requesting a waiver of **signed** authorization, describe why it would be impracticable to obtain the subject's signed authorization for use/disclosure of this data: phone screen for potential subjects, focus group will be verbally consented.

The investigator assures that the protected health information for which a Waiver of Authorization has been requested will not be reused or disclosed to any person or entity other than those listed in this application, except as required by law, for authorized oversight of this research study, or as specifically approved for use in another study by an IRB.

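### Does the enrolment target of 150 fall short of the cohorts the protocol describes?

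*Combined protocol and SAP*

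**What the plan says.** Section III, item 1 (Targeted Enrollment) reads "Targeted for enrollment at Yale for this protocol: 150". The next line, a template prompt beginning "If this is a multi-site study, give the total number of subjects targeted across all sites", is not filled in.

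The cohorts are described elsewhere. Aim 1a (end of item 3, Background) has "focus groups with up to 40 16-19-year old high school students", "focus groups with up to 20 18-25-year-old young adults", up to 20 interviews with people aged 16-25, up to 20 with treatment providers, and focus groups with up to 20 stakeholders. Aim 1b is the pilot of 30 adolescents. Aim 1c adds "focus groups with 50 School Based Health Alliance affiliates and 30 adolescents from the Youth Advisory Council". Item 6 (Subject Population) repeats these sizes, for example "50 adults (19-80) who are affiliates of the SBHA will be recruited over the course of two years". Section III, item 3 (Recruitment Procedures) adds: "The research study team will carry out all recruitment procedures".

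The local focus groups are listed twice in item 4 (Research Plan): once under the formative year, and again under the pilot year as "conducting 8 focus groups of 5 adolescents each (n=40), aged 16-19 and 4 focus groups of 5 young adults each (n=20").

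**The concern.** A reader who adds the cohorts gets 230 and finds only 150 in the enrolment line. The study team recruits and consents the Convention participants under this protocol, so leaving them out is not obviously right, and no line gives a grand total. If the pilot-year listing of the local focus groups were a second round of 60 people, the total would be 290.

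The worry is practical. The pilot comes late in the sequence and is the only cohort with baseline and post-play measurements. If 150 were a ceiling on everyone, the earlier cohorts could use it up, leaving the sponsor to over-enrol or shrink the pilot. The annual summary to the IRB also reports the number enrolled, which is hard to set against a target of unclear scope.

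**Working it through.** The inputs are the cohort sizes in aims 1a-1c, confirmed in item 6.

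| Cohort | Size | Aim |
|---|---|---|
| Adolescent focus groups, 16-19 | up to 40 | 1a |
| Young adult focus groups, 18-25 | up to 20 | 1a |
| Interviews, 16-25, in treatment | up to 20 | 1a |
| Interviews, treatment providers | up to 20 | 1a |
| Stakeholder focus groups | up to 20 | 1a |
| Pilot | 30 | 1b |
| School-based health affiliates, Convention | 50 (25 in each of 2 years) | 1c |
| Youth Advisory Council, Convention | 30 (15 in each of 2 years) | 1c |

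**Reproducing 150.** Aims 1a and 1b together: 40 + 20 + 20 + 20 + 20 + 30 = 150, an exact match.

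**All cohorts.** 150 + 50 + 30 = 230, and 230 - 150 = 80. That difference is aim 1c and nothing else.

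**How far the match can be trusted.** The sizes are round numbers, so chance matches are easy. Of all subsets of the eight cohorts, 13 sum to 150. One is adolescent focus groups, pilot and both Convention cohorts: 40 + 30 + 50 + 30 = 150. The match therefore shows that 150 is consistent with the local cohorts, not that it was derived from them.

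**Ceiling or headcount.** The five aim 1a cohorts are maxima. The Convention groups meet once a year for two years, and the same people may return. If all of the second year's 15 + 25 = 40 were returners (an assumption), there would be 230 - 40 = 190 different people, 40 above 150. So 230 is a maximum number of participations.

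**Second round of focus groups.** This reading gives 230 + 60 = 290, and 290 - 150 = 140. The documents are against it. Item 4 describes eight adolescent groups over six months, each meeting once. Item 6 gives 8 groups (40 people) and 4 groups (20 people) for the study as a whole. The timeline in item 2 puts the conduct of focus groups in Year 1 only. The pilot-year entry is a repeated listing.

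**Would the pilot be crowded out?** If 150 covers the local cohorts, the formative work takes 40 + 20 + 20 + 20 + 20 = 120 and the pilot's 30 brings it to 150, so the pilot fits. If 150 covered everyone, 120 plus the first Convention's 40 would make 160 before the pilot. For that to do harm, every cohort must also fill to its maximum and enrolment must stop at 150. The documents call 150 a target and state no such stop.

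**Use of 150.** Item 12 (Statistical Considerations) contains no sample-size or power statement based on it. The pilot size is 30 in the aims, in item 4 and in item 6, where 2 groups of 3 plus 6 groups of 4 give 6 + 24 = 30.

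**The case for a change.** The best case for a change is that the line asks for enrolment under this protocol, and Convention participants are plainly subjects of it. They appear in the Subject Population and eligibility sections, Youth Advisory Council members give assent or consent to the study team by telephone, and both Convention groups are paid. If 150 leaves them out, 80 participations, some by minors, have no place in the enrolment line. Even if every Convention participant returned, 190 people exceeds 150.

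Part of this stands. The protocol does not say which cohorts 150 covers, and the local reading is an inference. But the inference is reasonable. The line specifies Yale, and item 4 mentions the Convention groups separately from those held locally. The national partner also helps to recruit the Convention groups and sends the invitations. The blank all-sites line proves little, since it applies only to multi-site studies and other template prompts are also unfilled. Nor are the 80 hidden from the IRB: their numbers are stated by cohort in the aims and in the Subject Population section. The annual summary is to include the number enrolled, but nothing says it is judged against 150.

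**Conclusion.** The concern does not call for a change. The addition to 230 is correct as a maximum, but the documents do not show that 150 is an error: it equals the local cohorts exactly, and the difference of 80 is exactly the Convention cohorts. The figures of 290 and 140 fall away, because the protocol's own counts describe one round of focus groups. The claim that the pilot would be displaced needs an enrolment stop that the protocol does not contain.

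What remains is an unlabelled figure and a duplicated list entry, both clerical. Anyone tracking enrolment can read each cohort's size from the aims. The pilot's 30 participants and their analysis are the same whichever way 150 is read. This conclusion rests on treating 150 as a target rather than a cap. Reading it as the local cohorts is plausible but not confirmed by the documents.
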